Social and Behavioral Sciences Human Research Protocol Template

V4: 8 Jul 2022

PRINCIPAL INVESTIGATOR: [name]

PROTOCOL TITLE:

1. **Full Title:** Acute effects of cigarette packaging and charcoal filtration on perceptions, use behaviors, and harm exposure (IRB# 849152)
2. **Brief Title:** SKY Pilot

INTRODUCTION AND PURPOSE:

The US Food and Drug Administration (FDA) has the authority to regulate tobacco products, including their marketing and design.¹ There is modest empirical support that using cigarettes with charcoal filters may reduce exposure to some toxic constituents,²⁻⁴ which could improve health outcomes for users of these products. However, studies have produced mixed conclusions about reduced harm resulting from use of charcoal filters, and it is further unclear if such effects occur with real world use of charcoal-filtered cigarettes, especially if marketed in misleading ways. The tobacco manufacturer Natural American Spirit (NAS) is using charcoal filters, combined with other misleading pack attributes (e.g., light colored packaging, brand name conveying 'lightness'), to promote a new cigarette product called 'Sky.' Although the Sky product marketing makes no explicit references to reduced harm, its marketing materials contain prominent implicit references to charcoal's purification properties. Although Sky is just one product, if this brand is commercially successful, other manufacturers may mimic NAS's marketing tactics to promote similar charcoal filtered cigarette products and implicitly mislead smokers about health risks.

This single laboratory session pilot study will examine the acute effects of cigarette filter type and packaging on initial product perceptions, use, and exposure. Forty adult daily smokers will be randomized to smoke two study-supplied commercially-available cigarettes interspersed by 45 minutes, completing pre- and post-cigarette carbon monoxide and questionnaire measures. We will use a 2 x 2 mixed factorial design to manipulate cigarette filter type (within-subject: charcoal vs. non-charcoal) and packaging (between-subject: light vs. dark).

OBJECTIVES:

This project will address the following specific aims:

Aim 1: Examine the acute effects of filter type on product perceptions, use behaviors, and exposure.

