Tobacco regulatory relevance. By examining the effects of cigarette filter type and pack color on product perceptions, use behaviors, and exposure, this work directly addresses multiple research priorities of the FDA Center for Tobacco Products (CTP), including behavior (how changes in design and packaging affect tobacco use behaviors and perceptions), marketing influences (how marketing impacts abuse liability and product initiation), and toxicity (how product design characteristics impact constituent exposure).

INNOVATION.

This project is innovative for several reasons. To our knowledge, this is the first formal study to address the effect of placing charcoal cigarettes in different packaging contexts, providing the FDA with evidence informing regulatory decisions regarding both cigarette design and marketing. We will study two industry-created packages, primarily defined by their color (black vs. white) and representing extreme ends along a continuum of implicit harm, thus expanding upon previous work using traditional colors (e.g., blue, red) to assess the impact of novel packaging on consumer reactions. By using identical cigarette rods that have different filter compositions, we will also be able to disentangle effects of cigarette design from packaging/other marketing. Finally, smokers will sample the product, simulating actual initial novel product use, rather than respond to product marketing only, building upon previous work on pack color effects using survey methods.¹⁵

CHARACTERISTICS OF THE STUDY POPULATION:

1. Target Population and Accrual:

We aim to enroll, defined as completing the informed consent process, 60 adult smokers from the greater Philadelphia region to obtain 40 eligible study completers (approximately 20 male and 20 female). Recruitment is anticipated to begin in August 2021 and will continue for 2 years. This accrual projection is based on our experience running similar studies with non-treatment seeking smokers requiring multiple visits. As this study consists of a single visit, we do not anticipate significant retention issues, though we do expect some individuals who enroll could be later be deemed ineligible or withdraw their participation.

2. Key Inclusion Criteria:

Eligible subjects will be:

1. Male and female smokers who are between 21 and 60 years of age and self-report smoking at least 5 cigarettes per day for at least the past 12 months.

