Brand appeal: Participants will be asked to complete a 6-item measure of brand appeal regarding their preferred brand and the two study-supplied cigarettes they smoked during their in-person session. They will be asked to rate the design of the brand of cigarette they currently smoke (or just tried) on the following 6 items: 1) stylish, 2) fashionable, 3) cool, 4) high quality, 5) attractive, and 6) appealing. Responses will be scored using a 7-point likert scale with anchors of “Strongly Agree” and “Strongly Disagree.”

Mouth-level nicotine exposure and compensatory smoking: We will collect and store the filters of the two cigarettes smoked during laboratory sessions for potential future analysis regarding mouth-level nicotine exposure (approximated using the biomarker, solanesol) and compensatory smoking (estimated via digital image analysis).

2. Group Modifications:

There will be no differences in study procedures or questionnaire administration; all participants will complete the same procedures and questionnaires following randomization to filter type and packaging conditions.

3. Method for Assigning Subjects to Groups:

Participants will be randomly assigned to smoke two study-supplied cigarettes from 4 possible combinations of filter type and packaging conditions:

1. Charcoal filter cigarette in light-colored pack (NAS Sky cigarette in NAS Sky pack [i.e., actual product])
2. Charcoal filter cigarette in black-colored pack (NAS Sky cigarette in NAS Black pack)
3. Non-charcoal filter cigarette in light-colored pack (NAS Orange cigarette in NAS Sky pack)
4. Non-charcoal filter cigarette in black-colored pack (NAS Orange cigarette in NAS Black pack)

Each participant will smoke one charcoal filtered and one non-charcoal filtered cigarette, in counterbalanced order (i.e., the within-subject condition), but the participant will be assigned the same package color for both cigarettes (i.e., the between subject condition). Randomization group (filter order and package color) will be determined via internal database and assigned prior to participants' arrival for the session.

4. Administration of Surveys and/or Process:

The following measures will be assessed by staff at the start of the laboratory session:

1. Session onset CO
2. Medical history
3. Height and weight
4. Cigarette brand characteristics

The following measures will be completed by participants prior to trying to smoking any laboratory cigarettes:

1. Demographics
2. EtOH

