To inform subjects prospectively of the use of deception/incomplete disclosure, we have included the following suggested consent language on our consent document (see Informed Consent document): "In some research studies, the investigators cannot tell you exactly what the study is about before you participate in the study. We will describe the tasks in the study in a general way, but we can't explain the real purpose of the study until after you complete these tasks. When you are done, we will explain why we are doing this study, what we are looking at, and any other information you should know about this study. You will also be able to ask any questions you might have about the study's purpose and the tasks you did. Though we may not be able to explain the real purposes of the study until after you complete the tasks, there are no additional risks to those that have been described in this consent form."

Upon completing the full survey, participants will be debriefed of the true study purpose. They will be told that we were specifically interested in understanding the effects of cigarette packaging and filter type on their perceptions and use of the product, and that we were initially vague about our procedures to avoiding biasing their responses toward the study manipulations.

5. Statistical Analysis:

Analytic plan. Main and interaction effects of filter and pack type will be analyzed using univariate analysis of variance (ANOVA) models in SPSS IBM Statistics v26. Primary outcomes are continuous, and based on previous work^{17,21,22} are expected to meet normality assumptions. Analyses will first include only main and interaction effects, then will include as covariates any baseline variables demonstrating a bivariate association of $p < 0.25$ with a given outcome measure.

Power analysis and sample size. A priori power analyses were conducted for primary aims using G*Power v3.1.9.2. These analyses determined that a target sample size of 40 will be adequate to detect a significant small-to-medium effect (partial $\eta^2 = .05$, $\alpha = 0.05$, within-subject correlation = 0.5) of the 2 x 2 between-within subject interaction on a univariate outcome with 80% power.

RISK/BENEFIT ASSESSMENT:

1. Risks:

The potential risks to participants, and their likelihood and seriousness, are minimal and described below. Participants can choose, as an alternative, to not enroll in this study.

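### The 80% power at N = 40 is for an interaction of about 0.92 SD, which the planned mixed ANOVA would show as partial eta-squared of about .17–.18, not the printed .05

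*Combined protocol and SAP*

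**What the plan says.** Under Study Procedures, 5. Statistical Analysis, the power paragraph reports an a priori calculation in G*Power v3.1.9.2. It concludes that a "target sample size of 40 will be adequate to detect a significant small-to-medium effect". The settings are "partial $\eta^2 = .05$, $\alpha = 0.05$, within-subject correlation = 0.5", and the claim is for detection "of the 2 x 2 between-within subject interaction on a univariate outcome with 80% power". The paragraph gives no SD and no raw difference, and it does not say against which variance .05 is defined.

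Other parts of the document bear on the reading:

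- The Analytic plan, directly above: "Main and interaction effects of filter and pack type will be analyzed using univariate analysis of variance (ANOVA) models".
- Study Design: a 2 x 2 mixed factorial, with pack varied between subjects and filter within subjects.
- Target Population and Accrual: "60 adult smokers from the greater Philadelphia region to obtain 40 eligible study completers", so 40 is the analysed number.
- Method for Assigning Subjects to Groups: "Randomization group (filter order and package color) will be determined via internal database", with no allocation ratio.
- Introduction and Purpose, on the status of the study: "This single laboratory session pilot study will examine the acute effects of cigarette filter type and packaging".

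**The concern.** In the ANOVA that the plan names, partial eta-squared has a fixed meaning: the interaction's share of interaction plus error variation. In a mixed design the error term for this interaction is the within-subject one, so the correlation between a person's two measurements is already inside it. A power calculation that takes the correlation as a separate input is instead working with an effect measured against the variance of a single measurement. With two measurements and r = 0.5, the same f² gives a noncentrality that differs by a factor of 2/(1 − 0.5) = 4 between the two scales.

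The sentence is the plan's only statistical justification for N = 40 and its only statement of what the Aim 3 test can detect. Someone who sets the ANOVA's reported partial eta-squared beside the printed .05 would think the study was well powered for effects it would usually miss, and would read too much into a null interaction.

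**Working it through.** **Inputs.** From the power paragraph: N = 40, partial eta-squared .05, alpha 0.05, r = 0.5. From Study Design: m = 2 measurements per person and two pack groups, so the interaction F test has 1 and 38 degrees of freedom. Assumed: 20 participants per pack, and a mixed ANOVA with a within-subject error term.

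**1. Reproduce the plan's figure.**

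- f² = .05/.95 = .0526, so f = .2294.
- Applying the correlation on top: lambda = f² × N × m/(1 − r) = .0526 × 40 × 2/.5 = 8.42. Power from the noncentral F(1, 38) is **80.7%**.
- At N = 38, lambda = 8.00 and power is 78.6%, so 40 is the smallest even N that reaches 80%.
- A simulation of 200,000 trials also gave 80.7%.

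The plan's 80% is therefore arithmetically sound on this scale.

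**2. Express the powered effect in SD units.** Cell deviations of ±f mean opposite filter effects of 2f = 0.459 SD in the two packs, a difference-in-differences of 4f = **0.918 SD** of a single measurement. Check: the within-person difference has SD sqrt(2(1 − r)) = 1 at r = 0.5, so a two-group comparison of differences has lambda = .918²/(1/20 + 1/20) = 8.42, as in step 1.

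**3. Express the same effect on the ANOVA's own scale.** Two conventions are in use, with denominators based on error df or on N:

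- lambda/(lambda + 38) = 8.42/46.42 = **.181**
- lambda/(lambda + 40) = 8.42/48.42 = **.174**

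The median sample value in the simulation was .183. The value moves with the correlation, for which .3 and .7 are illustrative:

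| r | lambda for 0.918 SD | ANOVA partial eta-squared (N / df convention) | power |
|---|---|---|---|
| .3 | 6.02 | .131 / .137 | 66.6% |
| .5 | 8.42 | .174 / .181 | 80.7% |
| .7 | 14.04 | .260 / .270 | 95.4% |

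**4. Take .05 as the ANOVA's own value.** The correlation is then already in the error term. Lambda = .0526 × 38 = 2.00 or .0526 × 40 = 2.11, and power is **28.1% or 29.3%**, whatever r is. At r = 0.5 this is a difference-in-differences of sqrt(2.00 × .1) = 0.447 SD or sqrt(2.11 × .1) = 0.459 SD, about half the effect that is powered.

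**5. Effects detectable at exactly 80% power.** The required lambda at 1 and 38 df is 8.27. At r = 0.5:

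- Interaction: sqrt(8.27 × .1 × 1) = 0.91 SD, with ANOVA partial eta-squared 8.27/48.27 = .171 or 8.27/46.27 = .179.
- Filter effect: sqrt(8.27/40 × 1) = 0.45 SD.
- Pack effect: sqrt(8.27 × .1 × 1.5/2) = 0.79 SD.

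**6. Sensitivity to allocation.** For the 0.918 SD effect, power is 80.3% with packs split 18/22 and 79.1% with 16/24. Nothing here turns on the unstated ratio.

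**The case against.** The strongest reply is that the paragraph is correct and decipherable. It lists N, alpha, effect size, correlation, test and software, and those inputs return 80%. The correlation matters only on the single-measurement scale; on the ANOVA's own scale it drops out and 80% is not obtained. One reading alone uses every printed input and gives the printed power. That stands: these are not two equally live readings, and the fault is one of labelling. What remains is that a reader must solve the calculation backwards to find this out, while the adjacent Analytic plan commits to an ANOVA in which the same symbol takes a different value.

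Three technical reservations also stand:

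- The .17–.18 depends on the convention used, so both values should be covered.
- It assumes a within-subject error term. The plan says only univariate ANOVA. If the 80 observations were treated as independent, the value would be 4.21/(4.21 + 80) = .05, with 4.21 = .0526 × 80. That would discard the within-subject factor in the plan's own mixed design.
- The figures apply to the unadjusted models, not to the second, covariate-adjusted step.

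It is also fair that this is a pilot and that no decision rule uses .05. That limits the remedy to wording. The filter and pack figures are a side point and do not bear on the label.

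A reader might infer something stronger: that the 80% is wrong, or that the study simply has 28–29% power. The documents do not support this. The 80% reproduces from the stated inputs, and 28–29% applies only to an effect whose ANOVA partial eta-squared is .05, which the listed correlation indicates was not the quantity entered.

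**Conclusion.** The effect size is mislabelled for the planned analysis; the power is not miscalculated. At N = 40 the plan has 80% power for a filter-by-pack difference-in-differences of about 0.92 SD (0.91 SD for exactly 80%). The mixed ANOVA would show this as partial eta-squared of about .17–.18 at r = 0.5. For an interaction with ANOVA partial eta-squared of .05, power is about 28–29%. The label small-to-medium describes the effect on the f = 0.23 scale, which the plan does not name.

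The SD and .17–.18 figures rest on equal packs, a within-subject error term and the plan's own r = 0.5; the 28–29% does not depend on r.

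A reader might also infer that the sample must grow, since about 152–154 participants would be needed for 80% power at an ANOVA partial eta-squared of .05. The documents do not set that value as the target on the ANOVA's scale, and the study is a pilot, so this point gives no ground for a larger N. It should still be corrected, because it changes what a null Aim 3 result can support.

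**What to change.** Keep N = 40 and replace the power sentence, for example with:

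> Assuming equal allocation to packs, a mixed ANOVA with a within-subject error term, alpha = 0.05 and within-subject correlation 0.5, 40 participants give 80% power for a filter-by-pack difference-in-differences of about 0.91 SD of a single measurement (f = 0.23 on the single-measurement scale; ANOVA partial eta-squared about .17–.18). Power for an ANOVA partial eta-squared of .05 is about 28–29%.

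The label small-to-medium should stay only if tied to f = 0.23 on that named scale. Optionally, add the filter effect (0.45 SD) and pack effect (0.79 SD) detectable with 80% power, since the paragraph gives a figure only for the interaction.

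The change is to wording alone: no extra participants, and no change to conduct or analysis. The downside is a less favourable stated sensitivity.

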Staff training will be overseen by the PI and consist of an initial explanation and review of the protocol, informed consent form, CRFs and laboratory tasks, data management system, and all study-specific SOPs. In addition, during a standardized training period, the duties of each staff member will be clearly outlined, and all applicable regulations will be reviewed. Training interactions will be documented in a training log, which will be maintained within the regulatory binder. Senior personnel will supervise junior staff and provide re-training as needed. All personnel working on this project will complete required training in the protection of human subjects and the protection of personal identifiable information (i.e. HIPAA) before interacting with study data or research participants. All human subject and privacy protections certifications will be maintained in the regulatory binder.

Until COVID-19 research operation restrictions at UPenn are removed, training will be conducted primarily via BlueJeans, a HIPAA-compliant platform used by Penn Medicine for video conferencing purposes. Conducting training via BlueJeans will ensure all training procedures are completed appropriately while meeting COVID-19 social distancing guidelines.

3. Access to Target Population / Recruitment

Using proven strategies from prior studies conducted at the CIRNA (previous [name] and [name] protocols) we will recruit participants from the greater Philadelphia region primarily through digital media (e.g., internet postings, television ads), and secondarily through print ads and contacting former study participants. Our team has been highly successful using these methods to recruit adult, non-menthol smokers.

4. Research Facilities

This single-session study will take place in the CIRNA at the University of Pennsylvania. The facilities available for this project include physio rooms, ventilated smoking laboratories, storage rooms, office space for study personnel, and data management facilities. The lab has 5 Carbon Monoxide devices (Vitalograph) and several laboratory-housed computers are available to conduct data processing. Data are maintained on a firewall protected, secure server with continual backup. Paper data and participant charts are stored in locked cabinets in a secured storage room.

5. Timeline and Feasibility

